7.3 Subject Population(s) for Analysis

Each participant who received the study drug will be included in the primary analysis regardless of study withdrawal for any reason. In the event of any study withdrawals, in secondary analysis we will examine the sensitivity of our results to the exclusion of patients who withdrew.

8 Safety and Adverse Events

8.1 Definitions

Unanticipated Problems Involving Risk to Subjects or Others (UPIRTSO)

Any unanticipated problem or adverse event that meets the following three criteria:

- Serious: Serious problems or events that results in significant harm, (which may be physical, psychological, financial, social, economic, or legal) or increased risk for the subject or others (including individuals who are not research subjects). These include: (1) death; (2) life threatening adverse experience; (3) hospitalization inpatient, new, or prolonged; (4) disability/incapacity persistent or significant; (5) birth defect/anomaly; (6) breach of confidentiality and (7) other problems, events, or new information (i.e. publications, DSMB reports, interim findings, product labeling change) that in the opinion of the local investigator may adversely affect the rights, safety, or welfare of the subjects or others, or substantially compromise the research data, **AND**
- Unanticipated: (i.e. unexpected) problems or events are those that are not already described as potential risks in the protocol, consent document, not listed in the Investigator's Brochure, or not part of an underlying disease. A problem or event is "unanticipated" when it was unforeseeable at the time of its occurrence. A problem or event is "unanticipated" when it occurs at an increased frequency or at an increased severity than expected, AND
- Related: A problem or event is "related" if it is possibly related to the research procedures.

Adverse Event

An untoward or undesirable experience associated with the use of a medical product (i.e. drug, device, biologic) in a patient or research subject.

Serious Adverse Event

Adverse events are classified as serious or non-serious. Serious problems/events can be well defined and include;

- death
- life threatening adverse experience
- hospitalization
- inpatient, new, or prolonged; disability/incapacity
- persistent or significant disability or incapacity
- birth defect/anomaly

and/or per protocol may be problems/events that in the opinion of the sponsor-investigator may have adversely affected the rights, safety, or welfare of the subjects or others, or substantially compromised the research data.

All adverse events that do not meet any of the criteria for serious, should be regarded as **non-serious adverse events**.

Adverse Event Reporting Period

For this study, the study treatment follow-up period is defined as 90 minutes following the last administration of study treatment.

Preexisting Condition

A preexisting condition is one that is present at the start of the study. A preexisting condition should be recorded as an adverse event if the frequency, intensity, or the character of the condition worsens during the study period.

General Physical Examination Findings

At screening, any clinically significant abnormality should be recorded as a preexisting condition. At the end of the study, any new clinically significant findings/abnormalities that meet the definition of an adverse event must also be recorded and documented as an adverse event.

Post-study Adverse Event

All unresolved adverse events should be followed by the sponsor-investigator until the events are resolved, the subject is lost to follow-up, or the adverse event is otherwise explained. At the last scheduled visit, the sponsor-investigator should instruct each subject to report, to the sponsor-investigator, any subsequent event(s) that the subject, or the subject's personal physician, believes might reasonably be related to participation in this study.

Hospitalization, Prolonged Hospitalization or Surgery

Any adverse event that results in hospitalization or prolonged hospitalization should be documented and reported as a serious adverse event unless specifically instructed otherwise in this protocol. Any condition responsible for surgery should be documented as an adverse event if the condition meets the criteria for an adverse event.

Neither the condition, hospitalization, prolonged hospitalization, nor surgery are reported as an adverse event in the following circumstances:

• Hospitalization or prolonged hospitalization for therapy of the target disease of the study, unless it is a worsening or increase in frequency of hospital admissions as judged by the clinical investigator.

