8.2 Recording of Adverse Events

At each contact with the subject, the study team must seek information on adverse events by specific questioning and, as appropriate, by examination. Information on all adverse events should be recorded immediately in the source document, and also in the appropriate adverse

event section of the electronic case report form (CRF). All clearly related signs, symptoms, and abnormal diagnostic, laboratory or procedure results should recorded in the source document.

All adverse events occurring during the study period must be recorded. The clinical course of each event should be followed until resolution, stabilization, or until it has been ultimately determined that the study treatment or participation is not the probable cause. Serious adverse events that are still ongoing at the end of the study period must be followed up, to determine the final outcome. Any serious adverse event that occurs during the Adverse Event Reporting Period and is considered to be at least possibly related to the study treatment or study participation should be recorded and reported immediately.

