8.3 Reporting of Serious Adverse Events and Unanticipated Problems

When an adverse event has been identified, the study team will take appropriated action necessary to protect the study participant and then complete the Study Adverse Event Worksheet and log. The sponsor-investigator will evaluate the event and determine the necessary follow-up and reporting required.

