8.3.1 Sponsor-Investigator reporting: notifying the Mayo IRB

The sponsor-investigator will report to the Mayo IRB any UPIRTSOs and Non-UPIRTSOs according to the Mayo IRB Policy and Procedures.

Any serious adverse event (SAE) which the Principal Investigator has determined to be a UPIRTSO will be reported to the Mayo IRB as soon as possible but no later than 5 working days after the investigator first learns of the problem/event.

The following information will be collected on the adverse event worksheet (and entered in the research database):

- Study ID
- Disease
- The date the adverse event occurred
- Description of the adverse event
- Relationship of the adverse event to the research (drug, procedure, or intervention*)
- Determination if the adverse event was expected
- The severity of the adverse event (severity scale described below**)
- If any intervention was necessary
- Resolution (was the incident resolved spontaneously, or after discontinuing treatment)
- Date of Resolution

The sponsor-investigator will review all adverse event reports to determine if specific reports need to be made to the IRB and FDA. The sponsor-investigator will sign and date the adverse event report when it is reviewed. For this protocol, only directly related SAEs/UPIRTSOs will be reported to the IRB.

* Relationship Index

The relationship of an AE to the Investigational Drug is a clinical decision by the sponsorinvestigator (PI) based on all available information at the time of the completion of the eCRF and is graded as follows:

1. Not related: a reaction for which sufficient information exists to indicate that the etiology is unrelated to the study drug; the subject did not receive the study medication or the temporal sequence of the AE onset relative to administration of the study medication is not reasonable or the event is clearly related to other factors such as the subject's clinical state, therapeutic intervention or concomitant therapy.

2. Unlikely: a clinical event, including laboratory test abnormality, with a temporal relationship to drug administration which makes a causal relationship improbable and in which other drugs, chemicals, or underlying disease provide plausible explanations.

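### The duty to report serious adverse events immediately ends 90 minutes after dosing although events are evaluated to discharge, and 8.3.1 restricts IRB reporting in a way that conflicts with the UPIRTSO definition

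*Combined protocol and SAP*

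**What the plan says.** **Reporting window.** The only text under the Adverse Event Reporting Period heading in section 8.1 is that "the study treatment follow-up period is defined as 90 minutes following the last administration of study treatment". Section 8.2 uses the same capitalised term to limit a duty: "Any serious adverse event that occurs during the Adverse Event Reporting Period and is considered to be at least possibly related" to the treatment or to participation is to be recorded and reported at once. The same section also states that "All adverse events occurring during the study period must be recorded", but the study period is not defined for this purpose. Participation is under 12 hours in the Study Summary and intraoperative in section 3.3. The Schedule of Events marks adverse event evaluation at Visits 2 and 3, and section 6.4 describes Visit 3 as record review up to hospital discharge.

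**What continues after 90 minutes.** Section 8.2 says "Information on all adverse events should be recorded immediately in the source document". Under section 8.3 the team must "complete the Study Adverse Event Worksheet and log", after which "The sponsor-investigator will evaluate the event and determine the necessary follow-up and reporting required". Section 8.1 adds "Any adverse event that results in hospitalization or prolonged hospitalization should be documented and reported as a serious adverse event" (with an exception for treatment of the target disease) and provides for follow-up of unresolved events and for later reports by the subject.

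**IRB reporting.** Section 8.3.1 opens by sending UPIRTSOs and Non-UPIRTSOs alike to the IRB under its policy, and requires an SAE judged to be a UPIRTSO to be reported "no later than 5 working days after the investigator first learns of the problem/event". Later in the same section, a sentence specific to this protocol restricts IRB reporting to SAEs and UPIRTSOs that are directly related. The UPIRTSO definition in 8.1 asks only for a possible relation to the research procedures.

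**The concern.** There are two independent problems; correcting one leaves the other.

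First, the protocol looks for adverse events until discharge but attaches its only immediate-reporting duty to the first 90 minutes. Staff who follow 8.1 and 8.2 would report a possibly related SAE at once if it began at 80 minutes, but would have no such duty if it began at 100 minutes. Section 1.5 describes a drug risk that arises days later: haemolysis after methylene blue in patients with G6PD deficiency. Section 4.2 excludes only deficiency documented in the history, so an undocumented case could be enrolled, and 10 of the 20 participants are assigned methylene blue (5.2).

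Second, one sentence of 8.3.1 promises the IRB every UPIRTSO and a later sentence of the same section narrows that. Because the narrower sentence is expressly specific to this protocol, staff could reasonably treat it as overriding the general rule and not report an event that meets the UPIRTSO definition.

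**Working it through.** The 90 minutes is a definition and not a derived figure, so there is no plan calculation to reproduce. The check is a comparison of the sections plus unit arithmetic.

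**1. Timing.** Inputs: the 90-minute period (8.1), haemolysis onset at two to five days (1.5), and participation under 12 hours (Study Summary).

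- Reporting period: 90 / 60 = 1.5 h.
- Haemolysis onset: 2 × 24 = 48 h to 5 × 24 = 120 h.
- Gap after the period closes: 48 − 1.5 = 46.5 h to 120 − 1.5 = 118.5 h.
- Onset relative to the length of the period: 48 / 1.5 = 32 times to 120 / 1.5 = 80 times.
- Gap after participation ends: more than 48 − 12 = 36 h. This is a lower bound, because participation starts before dosing and lasts less than 12 h.

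The named late risk therefore falls wholly outside both the reporting period and the stated participation.

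**2. Deadline stated in the protocol for a possibly related SAE.**

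| Type of SAE | Onset within 90 minutes | Onset from 90 minutes to discharge |
|---|---|---|
| UPIRTSO | Immediate (8.2), and IRB within 5 working days (8.3.1) | IRB within 5 working days (8.3.1) |
| Not a UPIRTSO | Immediate (8.2) | None stated |

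The last cell is the gap. Section 8.3 leaves the reporting decision to the sponsor-investigator without a time limit. The prolonged-hospitalization rule in 8.1 gives no time limit either. Haemolysis would ordinarily fall in this cell if it were serious: it is a described risk, so it is normally not unanticipated and the 5-working-day rule would not usually apply.

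**3. Relatedness threshold for the IRB.**

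| Place | Threshold |
|---|---|
| 8.1, UPIRTSO definition | Possibly related |
| 8.3.1, opening sentences | All UPIRTSOs, with no further limit |
| 8.3.1, protocol-specific sentence | Directly related only |
| 8.3.1, Relationship Index | Not related, Unlikely, Possible, Probable, Definite |

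Grades that correspond by name to directly related: 0 of 5. Take an SAE that is unanticipated and graded Possible. It meets all three UPIRTSO criteria in 8.1, so the opening of 8.3.1 sends it to the IRB within 5 working days. On its natural reading, the later sentence withholds it. The contrast with 8.2, which also uses at least a possible relation, is weaker evidence, because 8.2 does not say who receives the immediate report.

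**The case against.** **On the window.** A short expedited period inside a longer recording period can be coherent, and any cut-off creates a before-and-after contrast. The 90-minute sentence speaks of a treatment follow-up period, so its link to the reporting period rests on the heading. Late events are still recorded in source, logged, evaluated and followed, and UPIRTSOs still reach the IRB within 5 working days. Haemolysis is described as typically self-limited, need not be serious, and would ordinarily not be IRB-reportable as a UPIRTSO even after a fix.

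Much of this is right, and it limits the point to the loss of the immediate duty. It does not remove it. If the 90-minute sentence does not define the reporting period, nothing does, and the duty in 8.2 has no window at all; the text needs repair on either reading. Haemolysis serves to show timing, not a missed IRB report. One qualification also stands: Non-UPIRTSOs are referred to an IRB policy that is not in the documents and may set its own deadline, so what can be said is that the protocol states none.

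**On the IRB threshold.** Directly related might be a loose restatement of the related criterion in 8.1, which would make this ambiguity and not contradiction. But the sentence is worded as a restriction for this protocol and uses a stronger word than possibly. Its natural reading excludes the grade Possible. Even on the kinder reading, the term is undefined and staff cannot apply it.

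**Conclusion.** Both parts hold, and they should be fixed. The immediate-reporting duty lapses 90 minutes after the last administration although evaluation continues to discharge, which leaves a possibly related, non-UPIRTSO SAE with no deadline stated in the protocol. The haemolysis risk in section 1.5 starts 46.5 to 118.5 hours after that point. Independently, 8.3.1 gives opposite answers on whether the IRB is told of an unanticipated SAE graded Possible.

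This rests on three readings: that the heading in 8.1 makes the 90 minutes the reporting period; that evaluation to discharge follows from the Visit 3 mark taken together with section 6.4, since the schedule gives no end time of its own; and that directly related is stricter than possibly related. The documents give no rate of undocumented G6PD deficiency or of late SAEs, so no number of affected cases is claimed. The descriptive efficacy results are not touched.

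**What to change.** - Reconcile 8.1, 8.2, 6.4 and the Study Summary. Define one Adverse Event Reporting Period and one study period, both agreeing with the adverse event evaluation already scheduled at Visit 3 to discharge.
- In 8.3.1, delete the sentence that restricts IRB reporting to directly related events. Alternatively, reword it so that reporting follows the 8.1 definition (serious, unanticipated and at least possibly related, within the existing 5 working days) and the IRB policy for Non-UPIRTSOs. Keep the unanticipated criterion, so that expected SAEs do not become IRB-reportable through this change.

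The cost is small but goes beyond wording. With the immediate duty running to discharge, more post-transplant events must be graded for relatedness and reported promptly, in about 20 patients whose charts are already reviewed to that point. Events that begin after discharge would still depend on the subject-report provision in 8.1.

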8.2 Recording of Adverse Events

At each contact with the subject, the study team must seek information on adverse events by specific questioning and, as appropriate, by examination. Information on all adverse events should be recorded immediately in the source document, and also in the appropriate adverse

event section of the electronic case report form (CRF). All clearly related signs, symptoms, and abnormal diagnostic, laboratory or procedure results should recorded in the source document.

All adverse events occurring during the study period must be recorded. The clinical course of each event should be followed until resolution, stabilization, or until it has been ultimately determined that the study treatment or participation is not the probable cause. Serious adverse events that are still ongoing at the end of the study period must be followed up, to determine the final outcome. Any serious adverse event that occurs during the Adverse Event Reporting Period and is considered to be at least possibly related to the study treatment or study participation should be recorded and reported immediately.

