1.5 Risks and Benefits

• The benefits of methylene blue:

Methylene blue causes vasoconstriction by inhibiting nitric oxide synthase and preventing subsequent activation of guanylyl cyclase in smooth muscle cells. This reaction increases systemic blood pressure and decreases vasopressor requirements for patients with vasoplegic syndrome. In LT surgery patients, hemodynamic stability without the requirements of vasopressors may allow immediate extubation at the end of the surgery and bypass the intensive care unit in the postoperative period, allowing faster recovery and improving outcomes. Advocates for early extubation have argued that it may be beneficial for the new organ graft to limit the exposure to mechanical ventilation. Kaisers et al reported the deleterious effects of positive end expiratory pressure (PEEP) on liver graft hemodynamics.

• The risks of methylene blue:

Common side effects include hypertension, discoloration of skin, hyperhidrosis, nausea, dizziness, headache, pain in limb, and abnormal urine color, hypersensitivity, hemolytic anemia

Medications which may accumulate with methylene blue due to inhibition of cytochrome P450 isozymes: Alfentanil, cyclosporine, digoxin, fentanyl, phenytoin, sirolimus, tacrolimus, warfarin.

Methylene blue is contraindicated in patients with glucose-6-phosphate dehydrogenase (G6PD) deficiency as it can result in a hemolytic response in patients with G6PD deficiency. The intravascular hemolysis typically occurs two to five days after drug administration and is typically self-limited.

Methylene blue may cause serotonin syndrome when used in combination with serotonergic drugs such as Selective serotonin reuptake inhibitors (SSRIs), serotonin and norepinephrine reuptake inhibitors (SNRIs), and monoamine oxidase inhibitors (MAOIs).

- The benefits of hydroxocobalamin: IV hydroxocobalamin is currently approved for cyanide poison treatment. Its ability to bind and inhibit the 3 main gasotransmitters (nitric oxide, carbon monoxide, and hydrogen sulfide) contributing to vasoplegic syndrome has made it a new treatment for intraoperative vasoplegic syndrome. Unlike methylene blue, it does not have the same implications in serotonin syndrome. Similar to the benefits of methylene blue on treating vasoplegic syndrome, hydroxocobalamin may play a major role to allow hemodynamic stability and early extubation in this particular LT population.

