6.3 Visit 2 (Randomization and Treatment – day of surgery)

- Liver Transplantation surgery (as per standard of care)
- Administration of Hydroxocobalamin or Methylene Blue

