6.4 Visit 3 (Off Study)

• Review of medical record will continue until study participants are discharged from the hospital

	Schedule of Events				
Study Activity	Visit la	Visit 1b	Visit 2	Visit 3	
Hydroxocobalamine or Methylene Blue			X		
Initial review of informed consent	Х				
Capacity to consent		Х			
Informed consent		Х			
Review of Medical Record	Х	Х		Х	
Concomitant Medications		Х	Х		
Adverse event evaluation			Х	X	

7 Statistical Plan

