3. Possible: a clinical event, including laboratory test abnormality, with a reasonable time sequence to administration of the drug but which could also be explained by concurrent disease or other drugs or chemicals; information on drug withdrawals may be lacking are unclear.

4. Probable: a clinical event including laboratory test abnormality, with a reasonable time sequence to administration of the drug, unlikely to be attributed to concurrent disease or other drugs or chemicals and which follows a clinically reasonable response on withdrawal (de-challenge): re-challenge information is not required to fulfil this definition.

5. Definite: a reaction that follows a reasonable temporal sequence from administration of the drug, or in which the drug level has been established in body fluids or tissues, that follows a known or expected response pattern to the suspected drug, and that is confirmed by improvement on stopping or reducing the dosage of the drug, and reappearance of the reaction on repeated exposure (re-challenge).

****** Severity Scale

The maximum intensity of an AE during a day should be graded according to the definitions below and recorded in details as indicated on the CRF. If the intensity of an AE changes over a number of days, then separate entries should be made having distinct onset dates.

1. Mild: AEs are usually transient, requiring no special treatment, and do not interfere with patient's daily activities.

2. Moderate: AEs typically introduce a low level of inconvenience or concern to the patient and may interfere with daily activities, but are usually ameliorated by simple therapeutic measures.

3. Severe: AEs interrupt a patient's usual daily activity and traditionally require systemic drug therapy or other treatment.

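### The plan finds adverse events by questioning and grades them by daily activities, but defines no post-dose contact with the patient and no grading rule that fits the operating room.

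*Combined protocol and SAP*

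**What the plan says.** **Finding events.** Section 8.2 requires: "At each contact with the subject, the study team must seek information on adverse events by specific questioning". It adds examination as appropriate. Section 8.1, under Post-study Adverse Event, also assumes a conversation: "At the last scheduled visit, the sponsor-investigator should instruct each subject to report" any later event thought to be related to the study.

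**Schedule.** Visit 2 (section 6.3) is the transplant operation with study drug given during it. Visit 3 (section 6.4) is titled as off study and has one listed procedure: "Review of medical record will continue until study participants are discharged from the hospital". The Schedule of Events has a separate row, "Adverse event evaluation", marked at Visits 2 and 3, with no method. Section 9.3 says all study data come from the EHR.

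**Time frame.** Section 8.1, under Adverse Event Reporting Period, sets treatment follow-up at 90 minutes after the last administration. Section 3.3 describes participation as intraoperative, and the Study Summary gives less than 12 hours.

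**Expected effects.** Section 1.5 lists common side effects of each drug. The methylene blue list includes "nausea, dizziness, headache, pain in limb"; the hydroxocobalamin list includes nausea and headache.

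**Severity.** Section 8.3.1 has three grades, each worded partly by interference with daily activities and partly by need for treatment. The top grade covers events that interrupt usual activity and "traditionally require systemic drug therapy or other treatment".

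**The concern.** The rule for finding events needs a patient who can answer, and no listed procedure after dosing provides one. Nausea, dizziness, headache and limb pain would then enter the data only through what clinical staff happened to chart. The study is open-label (section 5.7) and the anesthesia team is told the assignment (section 5.3), so unsolicited charting could differ between arms for reasons unrelated to the drugs.

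The severity scale was written for people going about ordinary life. Applied to an event on the operating table, half of each definition has no meaning, and two investigators could reasonably assign different grades.

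This bears on more than a table. Severity is a required worksheet field (section 8.3.1), and section 8.1 makes greater than expected frequency or severity one ground for calling an event unanticipated, which feeds the decision to report to the IRB. The pilot is also meant to supply descriptive data for a larger study (section 7.1).

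**Working it through.** The plan gives no figure for this point, so the check compares sections and counts terms.

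**Step 1. Is there a listed point after dosing where questioning can occur?**
- Visit 2: surgery and dosing. That the patient is anesthetized is an inference. Dosing is intraoperative, and section 2 places early extubation after surgery. No duration of anesthesia is stated.
- Visit 3: record review is the only procedure in section 6.4. The evaluation mark in the schedule has no method attached.
- Result: no interview or examination is listed after dosing, while sections 8.2 and 8.1 both presuppose one. The sections are inconsistent on contact; they do not rule it out.

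**Step 2. How many listed effects depend on the patient's own report?** Terms are counted from section 1.5. Sorting them is a judgment. A term named for both drugs is counted once for each.
- Methylene blue, 10 terms. Self-reported: nausea, dizziness, headache, limb pain, so 4/10 = 40%. Observable or measurable: hypertension, skin discoloration, sweating, urine color, hypersensitivity, hemolytic anemia, so 6.
- Hydroxocobalamin, 7 terms. Self-reported: nausea, headache, so 2/7 = 29%. Observable or measurable: raised blood pressure, erythema, rash, lymphocyte count, urine color, so 5.
- Together: (4 + 2)/(10 + 7) = 6/17 = 35% self-reported, and (6 + 5)/17 = 11/17 = 65% observable or measurable.

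The self-reported share differs between the drugs, so reliance on charting does not fall equally on the two lists.

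**Step 3. Can the severity scale be applied during surgery?**
- Grades that refer to daily activities: 3 of 3. This part cannot be assessed under anesthesia.
- Grades that also have a treatment-need element: 3 of 3 (no special treatment; simple measures; systemic drug or other treatment). This part can be assessed.
- The line between simple measures and systemic drug therapy is not drawn. Section 4.1 requires that vasopressors are already in use at entry, so intravenous treatment is routine here and the line matters.
- The scale grades the worst intensity in a day and provides for change over several days, whereas treatment follow-up is 90 minutes.
- No grade lies above severe.
- Result: grading is possible through one of the two elements, but not reproducibly.

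**Step 4. What is the status of a symptom reported after extubation?** Section 8.2 requires recording of all events in the study period, and immediate reporting of related serious events in the Adverse Event Reporting Period. The 90-minute figure, the intraoperative participation and the Visit 3 evaluation running to discharge give different end points. A headache first reported on the ward falls outside the first two and inside the third.

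**The case against.** The strongest reply is that the plan already contains what is needed. The Visit 3 evaluation has its own row, separate from record review, and so may be meant as a contact. The rule in section 8.2 reads "the study team must seek information on adverse events by specific questioning and, as appropriate, by examination", so questioning is not the only route, and the section also calls for recording related signs, symptoms and abnormal results. Safety is not a primary endpoint (section 3.6), and 20 patients can be listed individually.

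Much of this stands, and it rules out four stronger conclusions that a reader might draw:
- *That the plan provides no contact with an awake patient.* The method at Visit 3 is unstated. Silence is not exclusion, and the section 8.1 instruction implies a contact.
- *That the listed side effects are missed.* Eleven of the 17 terms do not need patient report, and the other six may be charted in a record reviewed until discharge.
- *That intraoperative events cannot be graded, or that nearly all treated ones become severe.* Every grade has a treatment-need element, the middle grade allows simple measures, and the severe definition joins treatment to interrupted activity.
- *That an arrest could not be told from a brief pressure change.* Section 8.1 classes death and life-threatening events as serious, and the worksheet records a description, any intervention and the resolution.

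The reply does not supply a method for Visit 3. Examination also needs a contact, and it would not reveal headache or limb pain. Nor does the reply make the daily-activities wording usable in surgery.

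**Conclusion.** The point holds as an inconsistency that should be corrected. Sections 8.1 and 8.2 require exchanges with the patient that section 6.4 and the schedule do not define. On the procedures listed, 6 of 17 effect terms (4 of 10 for methylene blue, 2 of 7 for hydroxocobalamin) depend on charting by staff who may know the arm. All three severity grades use a criterion that does not apply under anesthesia, and none lies above severe; the seriousness classification partly makes up for that.

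The effect is on the adverse event description and on severity-based reporting judgments. The hemodynamic primary endpoint is untouched. The conclusion assumes that patients are anesthetized from dosing to the end of surgery, that the sorting of terms in Step 2 is accepted, and that some clinical staff know the assignment. The documents do not show that any event would in fact go unrecorded.

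**What to change.** 1. In section 8.3.1, replace the activity-based scale with one that can be applied under anesthesia and has life-threatening and fatal grades, for example CTCAE grades 1 to 5. This costs wording and a REDCap field.
2. In section 6.4 and the Schedule of Events, define the Visit 3 adverse event evaluation as one brief bedside contact by existing study staff before discharge, where the patient can respond. Use one fixed checklist of all section 1.5 effects, asked the same way in both arms, and give the section 8.1 instruction then. For patients who cannot respond, or if no contact is wanted, state that capture is chart-only and amend sections 8.1 and 8.2 to match.
3. In section 8.1, reconcile this with the 90-minute period, so that the status of events reported later is defined. Align section 3.3 and the participation time in the Study Summary.

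The contact takes a few minutes for each of up to 20 patients; at an assumed five minutes, 20 × 5 = 100 minutes in all. Section 12.1 describes the grant as covering coordinator time for consent, so this time has to be found. The changes need an IRB amendment. More minor events will be recorded, and the report should say that they were solicited.
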